#### 4.2 Randomization

Eligible participants will be randomized in a 1:1 allocation to Intervention (i.e., immediate *APOL1* gene testing and ROR to participant and provider) and Control arms (delayed *APOL1* gene testing and ROR to participant and provider). Randomization will be stratified by clinical site with a random block size within site.

Participants that are randomized to receive immediate *APOL1* ROR will simultaneously be randomized to the PGx substudy intervention (i.e., immediate PGx gene testing and ROR to participant and provider) or the PGx control (delayed PGx gene testing and ROR to participant and provider) using a 1:1 allocation ratio. Participants from PGx substudy participating sites that test negative for *APOL1* will proceed into the PGx substudy under their assigned PGx treatment arms, while participants from non-participating sites of the substudy and participants that test positive for *APOL1* will be excluded from the substudy and receive delayed PGx gene testing and ROR.

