#### Providers

- The return of PGx genetic testing results to patient providers via standard site-specific laboratory return of results methods at approximately the same time or after participants have received their PGx testing results.

- Where possible, a CDS provider alert for actionable phenotypes when a relevant medication is or may be ordered that indicates the participant's genetic results, the predicted phenotype (i.e., efficacy of various hypertension medications), and treatment recommendations at approximately the same time or after participants have received their PGx testing results.

**Tables 2 and 3** describe the genes, variants, and phenotypes for the PGx substudy. The PGx sub-study will examine the efficacy of providing genetic information for two gene-drug pairs. The first gene-drug pair is *YEATS4* and thiazide diuretic efficacy, and focuses on first-line antihypertensive therapy in African Americans. The second gene-drug pair is *NAT2* and hydralazine. Hydralazine is not first line therapy, but is used in the treatment of resistant hypertension. GUARDD-US will include patients with both hypertension and resistant hypertension. Neither gene-drug pair is presently recommended by CPIC, but both have significant evidence supporting their relationship in populations that include individuals of African ancestry which is summarized in **Appendix B**.

**Table 4** describes the PGx recommendations to be given for actionable genotypes. Each recommendation will be provided in the laboratory return of results and via a CDS alert, where available, that will be activated when a provider prescribes a medication that is not recommended based on the participant's genotype. Please see section 7.6 for more details.

**Table 2.** Genes and gene variants to be tested in the PGx substudy.

Gene	Variant
NAT2	rs1801279, rs1801280, rs1799930, rs1799931
YEATS4	rs7297610

**Table 3.** PGx genotypes, phenotypes, and predicted genotype frequencies.

Gene	Genotyping Result	Predicted Phenotype	Phenotype Frequency
NAT2	1 or more copy of *4	Reduced Hydralazine Efficacy	0.50
NAT2	2 copies of *5, *6, *7, *14 b	Increased Hydralazine Efficacy	0.50
YEATS4	T/T or T/C	Reduced Thiazide Efficacy	0.51
YEATS4	C/C	Standard Thiazide Efficacy	0.49

**Table 4.** PGx recommendationsa

Goal (Drug Class)	Gene	Genotype	Recommendation

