## **7.5 Specimen Transfer and Genetic Testing Procedures**

All collected specimens should be clearly marked with the participant ID and all other required fields according to the instructions in the MOP, and delivered to a designated laboratory. Samples from Intervention arm participants will be processed by the laboratory as soon as possible using analytically validated *APOL1* and PGx gene testing procedures. For Control arm samples, designated laboratories will either extract DNA as soon as possible after sample receipt, and store the DNA for later analysis or store the sample and extract DNA after the Control participant has completed the 6 month follow-up assessment. Control Arm DNA samples will be processed as soon as possible after the 6 month visit using analytically validated procedures. Genes to be tested for the PGx substudy along with genotyping results and predicted phenotypes are described in Section 7.1. Details of sample storage and transport will be presented in the MOP. All laboratories in GUARDD-US are Clinical Laboratory Improvement Amendments (CLIA)-certified for high complexity.

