## **7.6 Return of Genetic Results**

The designated laboratories will transfer participant genetic testing results to the IGNITE PTN Coordinating Center (CC) as soon as possible and follow standard site-specific procedures for return of results to providers. Genetic results will be imported into the study database and the site EHR, where available. The study database will notify study personnel when a participant's lab results are ready to be returned to the participant.

Participants will receive *APOL1* and/or PGx results via phone and/or in-person. Research Coordinators should call participants at the appropriate time (see **Figure 1** and **Tables 5-7**), follow the ROR script (provided in the MOP), and end with a speak back in which participants will explain their results back in order to ensure comprehension. Research Coordinators should note the date, time, and completion status of all RORs in the study database. All participants will receive their genetic test results with lay explanations in writing and an educational booklet explaining their results and genetic risks via mail and/or secure email. Research Coordinators will offer all participants the option to speak by phone or in person with a study genetic counselor about their results. If a participant wants to speak with a genetic counselor, the Research Coordinator should contact the genetic counselor for their site on behalf of the patient, and the genetic counselor should reach out to the patient for counseling.

Providers may be notified of participant results via standard site-specific laboratory return of results methods and, where possible, a CDS within the electronic health system as described in Section 7.8. The genetic testing results should also be stored in the participant's medical records.

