## **7.10 Schedule of Activities**

Providers should be recruited and asked to complete the baseline survey as soon as possible after site activation. CDS alerts for providers should be activated as soon as lab results are entered into the electronic health record.

**Tables 5, 6, and 7** describe the participant schedule of events for GUARDD-US.

**Table 5.** Schedule of participant activities up to randomization for sites.

Activities	Prior to baseline	Baseline visit
Recruit participants	X	X
Screen potential participants for interest/eligibility	X	X
Contact participant to schedule baseline visit	X	X
Obtain consent	X	OR X
Obtain BP & pulse & return BP results to participant		X
Distribute educational booklet/s to participant		X
Administer baseline participant survey		X
Perform sample collection		X
Randomize to APOL1 treatment at end of baseline visit & notify patients of their randomization assignment		X

**Table 6.** Schedule of activities following participant baseline visit for sites participating in the PGx substudy.

Activities	CONTROL GROUP				INTERVENTION GROUP											
					APOL1 Positive				APOL1 Negative PGx Control Group				APOL1 Negative PGx Intervention Group			
	After Baseline & before 3M visit	3M visit (+8 wks)	6M visit (+8 wks)	After 6M visit	After Baseline & before 3M visit	3M visit (+8 wks)	6M visit (+8 wks)	After 6M visit	After Baseline & before 3M visit	3M visit (+8 wks)	6M visit (+8 wks)	After 6M visit	After Baseline & before 3M visit	3M visit (+8 wks)	6M visit (+8 wks)	After 6M visit
Participant surveys, BP & pulse measurements, & return of BP results to participant		X	X			X	X			X	X			X	X	
APOL1 testing conducted at laboratory				X	X				X				X			
Return APOL1 test results to participant verbally and with written explanation				X	X				X				X			
Give educational booklet for APOL1 results via mail or secure email				X	X				X				X			
PGx testing conducted at laboratory				X	X				X				X			
Return PGx Results verbally and with written explanation				X				X				X	X			
Give educational booklet for PGx results via mail or secure email				X				X				X	X			

**Table 7.** Schedule of activities following participant baseline visit for sites participating not in the PGx substudy.

Activities	CONTROL GROUP				INTERVENTION GROUP			
	After Baseline & before 3M visit	3M visit (+8 wks)	6M visit (+8 wks)	After 6M visit	After Baseline & before 3M visit	3M visit (+8 wks)	6M visit (+8 wks)	After 6M visit

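### Section 4.2 delays PGx testing for PGx Control and APOL1-positive Intervention participants, but Section 7.5 and Table 6 test them before 3 months, and Sections 7.6 and 7.10 contain no hold on the results

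*Combined protocol and SAP*

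**What the plan says.** All references are to the combined protocol and SAP.

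**When PGx testing is done**
- Section 4.2 assigns half of the Intervention arm to the "PGx control (delayed PGx gene testing and ROR to participant and provider". It adds that "participants that test positive for *APOL1* will be excluded from the substudy and receive delayed PGx gene testing and ROR".
- Section 7.5 makes no such distinction: "Samples from Intervention arm participants will be processed by the laboratory as soon as possible using analytically validated *APOL1* and PGx gene testing procedures".
- Table 6 (Section 7.10), in the row "PGx testing conducted at laboratory", marks the period before the 3-month visit for all three Intervention subgroups: APOL1 Positive, PGx Control and PGx Intervention. Only the main Control group is marked after the 6-month visit.

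**When PGx results are returned**
- Table 6 puts return to participants after the 6-month visit for main Control, APOL1 Positive and PGx Control. For PGx Intervention it comes before the 3-month visit.
- Section 7.1 (PGx, Providers) has the provider result and the PGx alert arrive "at approximately the same time or after participants have received their PGx testing results".

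**When results reach the EHR and the alerts**
- Section 7.6: "Genetic results will be imported into the study database and the site EHR, where available". No time is given and no group is excepted.
- Section 7.10: "CDS alerts for providers should be activated as soon as lab results are entered into the electronic health record". Section 7.8 includes PGx alerts among those that sites are to build.

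**The concern.** The endpoint of both the main study and the substudy is change in SBP at 3 months, and both contrasts depend on who has which genetic result before then. For the main Control arm the protocol gives the strongest protection available: the sample is not genotyped until after the 6-month visit, so no result exists to be seen. Section 4.2 appears to offer PGx Control and APOL1-positive Intervention participants the same protection. Section 7.5 and Table 6 remove it.

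Once the result exists, only a release rule keeps it from the provider, and the sections that govern data flow contain none. Two contrasts are then exposed:
- **PGx substudy.** A PGx Control provider who sees the result can act on it, which moves the control arm towards the intervention arm.
- **Main study.** Among APOL1-positive participants, those in Intervention at PGx sites would have PGx guidance available, while those in main Control would not have been tested. The primary difference would then mix knowledge of APOL1 status with PGx-guided prescribing.

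**Working it through.** **1. Testing time, side by side**

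| Group (PGx sites) | Section 4.2 | Section 7.5 | Table 6 testing | Table 6 return |
|---|---|---|---|---|
| PGx Intervention | immediate | as soon as possible | before 3 months | before 3 months |
| PGx Control | delayed | as soon as possible | before 3 months | after 6 months |
| APOL1-positive Intervention | delayed | as soon as possible | before 3 months | after 6 months |
| Main Control | not stated for PGx | after 6 months | after 6 months | after 6 months |

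In rows 2 and 3, Section 4.2 cannot be followed together with Section 7.5 and Table 6.

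**2. Release rule, side by side**
- Section 4.2 delays return to the provider as well as the participant, Section 7.1 ties the provider to the participant's return, and Table 6 dates that return. Together they hold rows 2 and 3 until after the 6-month visit.
- In Section 7.6 the laboratory's transfer to the coordinating center is to be prompt. The EHR import has no date and no exception.
- Section 7.10 ties alerts to entry in the EHR, whereas Section 7.1 ties them to participant return. If an early result is imported, the two sections give different activation dates.

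**3. Number of participants affected**

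Inputs from Sections 4.4 and 9.1: 4400 participants at PGx sites, 1:1 allocation, 14% APOL1 positive. Table 7, for the other sites, has no PGx row, so only PGx sites are counted.
- Substudy: 4400 × 0.5 × 0.86 = 1892, or 946 per arm, as the plan states. PGx Control is therefore 946.
- APOL1-positive Intervention at PGx sites: 4400 × 0.5 × 0.14 = 308, against a planned 469 APOL1-positive participants per arm in the main study.

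**4. The plan's own power**

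Inputs from Section 9.1: difference 3.1 mm Hg, SD 20 mm Hg, two-sided 5%, 10% lost to follow-up.
- Evaluable per arm: 946 × 0.9 = 851.
- Standard error: 20 × √(2/851) = 0.970 mm Hg.
- Noncentrality: 3.1 / 0.970 = 3.20. Power from the noncentral t distribution is 89%, which matches the stated figure of approximately 90%.

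**5. Illustration of dilution**

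Suppose a share c of PGx Control obtains the full PGx effect before 3 months. The documents give no value of c, so these shares are assumed. The expected difference becomes 3.1 × (1 − c).

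| c (assumed) | Difference, mm Hg | Power |
|---|---|---|
| 0 | 3.10 | 89% |
| 10% | 2.79 | 82% |
| 20% | 2.48 | 72% |
| 30% | 2.17 | 61% |

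**The case against.** The strongest reply is that the specific rule governs. Section 7.1 expressly ties provider return and the PGx alert to participant return, Section 4.2 delays return to the provider, and Table 6 dates it. The alert sentence in Section 7.10 applies only once a result is in the EHR and does not name PGx. Section 7.6 does not say when import happens. A reader might infer that Sections 7.6 and 7.10 order these results to be released on arrival. They do not, and that reading has to be set aside.

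The synopsis and Section 4.1 also define the PGx arms by immediate or delayed return, not by the date of genotyping. Testing early and holding the result is compatible with that definition, so the testing conflict alone need not harm the contrast; the error may lie in Section 4.2's reference to testing. Finally, Section 7.8 says that alert details go to sites separately, and Section 7 defers further detail to the manual of operations. A hold may exist there, and its absence in practice cannot be inferred from this document.

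All of that stands, and it limits the point to a risk left open. It does not remove the point. Section 7.8 brings PGx alerts within the alerts that Section 7.10 activates. Section 7.10 uses a different trigger from Section 7.1, and Section 7.6 has no exception by PGx arm. Early testing makes the hold necessary, and the sections that control the data flow do not state it.

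The dilution figures also deserve caution. They give a PGx Control participant whose provider sees the result the whole effect of the PGx intervention, although that intervention includes verbal and written return to the participant. Provider-only exposure would probably do less.

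**Conclusion.** The testing-time contradiction is direct: Section 4.2 conflicts with Section 7.5 and Table 6 for about 946 PGx Control and 308 APOL1-positive Intervention participants. Early provider access to their results is possible under Sections 7.5, 7.6 and 7.10, is not prescribed, and would contradict Sections 4.2 and 7.1.

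For the substudy, the cost would be dilution: power of 82%, 72% or 61% instead of 89% at assumed shares of 10%, 20% or 30% receiving the full effect. These figures illustrate sensitivity and do not estimate how often results were seen.

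For the main study, the direction of concern is clear, because PGx guidance would be available on the Intervention side only, but no size can be given. A reader might multiply the share at PGx sites by the frequency of T carriers and the genotype gap in thiazide response in Appendix B: 4400/6750 × 0.51 × (13.1 − 9.6) = 1.2 mm Hg. The documents do not support that as an estimate or a bound. The gap is a difference in response to one drug between genotypes, not the benefit of acting on a result. Appendix B says that this drug was not compared directly with the alternative class. How many participants would otherwise be prescribed a thiazide is not given, and the hydralazine pair is left out.

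**What to change.** 1. Reconcile Section 4.2 with Section 7.5 and Table 6, so that one time is given for PGx testing in PGx Control and in APOL1-positive Intervention participants.
2. In Sections 7.6 and 7.10, state that PGx results of these two groups are not entered in the site EHR, sent to providers or used to activate alerts before the return date that follows from Sections 4.2 and 7.1 and Table 6.
3. Report, by arm, how many such results were visible in the EHR before the 3-month visit. This remains informative even if enrollment is well advanced.

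The cost is a few sentences, a release check at the laboratory or coordinating center, and one descriptive count. Sample size, significance level and the primary analysis do not change. An analysis that drops whole sites where early visibility occurred is not advised, because it would select on an event after randomization.

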#### **4.3 Blinding**

GUARDD-US randomization assignments will not be blinded to any participants, providers or study personnel because: 1) it is impossible to mask participants from the intervention testing and ROR, 2) research staff often receive questions from participants about the interpretation and risk associated with the participant's genetic results during the administration of surveys, and 3) resource limitations make hiring additional blinded staff to measure blood pressure impractical. To minimize bias in the measurement of the primary outcome, randomization assignments will only be revealed after baseline survey responses and blood pressure readings have been collected, digital blood pressure devices (such as Professional Intellisense Blood Pressure Monitor OMRON-907) will be used to measure blood pressure, and blood pressure will be measured as the mean of the second and third blood pressure readings for each participant at each visit. Manual blood pressures may be collected if necessary.

#### **4.4 Sample Size**

Main Study: GUARDD-US will randomize approximately 6750 individuals with approximately 3375 individuals in the Control Arm and 3375 in the Intervention arm. Assuming a 14% prevalence of *APOL1* positive individuals, a sample size of 6700 for the randomized population would result in 938 *APOL1* positive individuals with at least 469 in each arm for the main study population. This sample size will detect a 3.5 mm Hg difference in the change in SBP between baseline and 3 months between Intervention - *APOL1* positive and Control - *APOL1* positive groups with 80% power. Since *APOL1* result data and SBP change data could be missing for various reasons, an approximately 50 individuals will be randomized in addition to the 6700 sample size. Therefore, the total randomization target is approximately 6750. Please see Section 9.1 for assumptions, clinical significance, and detailed power and sample size calculations.

PGx Substudy: Of the approximately 6750 participants in the GUARDD-US study, approximately 4400 will also be at a site participating in the PGx substudy. A sample size of 4400 with a 14% prevalence of *APOL1* positive individuals would result in 1892 participants for the PGx substudy (Intervention – *APOL1* negative participants) with 946 participants in the PGx Control and PGx Intervention arms. This sample size will detect a 3.1 mm Hg difference in the change in SBP from baseline to 3 months between the PGx Intervention group and PGx Control group with approximately 90% power. Please see Section 9.1 Sample Size Determination for assumptions, clinical significance, and detailed power and sample size calculations.

## 5. STUDY POPULATION

### 5.1 Inclusion Criteria

- Self-reported African ancestry
- English Speaking
- Age 18-70 years
- Have diagnosis of hypertension
  - Diagnosis of hypertension is defined by either:
    - ICD10 diagnosis codes (i.e., I10; I11.x; I12.x; I13.x; I16.x) OR
    - On active antihypertensive therapy for indication of hypertension OR
    - Having systolic blood pressure of 140 mm Hg or greater in at least 2 of the last 3 consecutive recorded values in the EHR OR
    - Having hypertension in the patient's medical record problem list
  - Have been seen at ≥1 time in past year at a participating primary care site
  - Either: 1) do not have diabetes and do not have CKD, or 2) have CKD; Participants with diabetes may be included as long as they also have CKD.
    - CKD is defined by:
      - A) ICD10 codes (i.e., N18.x; E08.22; E09.22; E10.22; E11.22; E13.22 (exclude Z94.0; N18.6; Z99.2)) OR
      - B) Microalbumin/proteinuria level >30 mg/g for 2 time periods ≥ 3 months. Values taken within 12 months of enrollment, unless 2 values are unavailable, then review within 24 months of enrollment.
        - 1) If there is only 1 proteinuria in E.H.R. (or if there are multiple and they are all within 3 months), any single proteinuria/microalbuminuria >30 mg/g would qualify
        - 2) If there are two or more proteinuria measures in E.H.R. that are at least 3 months apart AND are >30 mg/g would qualify
          - a. Even if there are multiple proteinuria measures in the E.H.R., and only two of them are >30 mg/g, but they are separated by at least 3 months would qualify
          - b. If there is only 1 proteinuria measure >30 mg/g and there are 2 or more proteinuria measures separated by 3 months within the prior 12 months would not qualify
        - 3) If there are not 2 proteinuria measures in 12 months, review within 24 months of enrollment.  
OR
      - C)  $15 \leq eGFR \leq 60$  ml/min for 2 time periods ≥ 3 months  
GFRs are taken within 12 months of enrollment, unless 2 values are unavailable, then review within 24 months.
        - 1) If there is only 1 GFR in E.H.R. (or if there are multiple and are all within 3 months), any single GFR between 15-60 would qualify
        - 2) If there are two or more GFRs in E.H.R. that are at least 3 months apart AND are between 15-60 would qualify
          - a. Even if there are multiple GFRs in the E.H.R., and only two of them are between 15-60, but they are separated by at least 3 months would qualify
          - b. If there is only 1 GFR between 15-60 and there are 2 or more GFRs separated by 3 months within the prior 24 months would not qualify
        - 3) If there are not 2 GFRs in 12 months, review within 24 months.
  - Diabetes is defined by:
    - HbA1c ≥ 6.5 at least one time in the last year OR

- ICD10 diagnosis codes (see Table 10, Appendix A) OR
- Having diabetes in the patient's medical record problem list

## 5.2 Exclusion Criteria

- Have diabetes, but no CKD.
- Are currently on dialysis (ICD 10 codes N18.6, Z99.2 and Z94.0)
- Have ESRD (eGFR<15 ml/min)
- Have a left ventricular assist device (LVAD)
- Have a terminal illness (specifically metastatic cancer, palliative care or hospice)
- Have patient-reported known pregnancy at time of enrollment
- Have had a liver, kidney, or allogeneic bone marrow transplant
- Too cognitively impaired to provide informed consent and/or complete the study protocol
- Institutionalized or too ill to participate (i.e. incarcerated, psychiatric or nursing home facility)
- Plan to move out of the area within 6 months of enrollment
- Not a current patient seeing a provider who cares for their hypertension (i.e., family medicine, internal medicine, nephrology, HIV provider, cardiology, hypertension specialists) at a participating site
- Previously participated in the GUARDD pilot study OR have previously undergone *APOL1* testing

